6.2 Rituximab

The most common (≥25%) adverse reactions in clinical trials for NHL and CLL were infusion reactions, fever, lymphopenia, chills, infection, asthenia, and neutropenia.

According to the package insert for rituximab, rituximab can cause:

- *Infusion reactions:* Rituximab can cause severe, including fatal, infusion reactions. Severe reactions typically occurred during the first infusion with time to onset of 30-120 minutes.
- Severe mucocutaneous reactions: These reactions include paraneoplastic pemphigus, Stevens-Johnson syndrome, lichenoid dermatitis, vesiculobullous dermatitis, and toxic epidermal necrolysis. The onset of these reactions has been variable and includes reports with onset on the first day of rituximab exposure.
- Hepatitis B virus reactivation: Hepatitis B virus (HBV) reactivation, in some cases resulting in fulminant hepatitis, hepatic failure and death, can occur in patients treated with drugs classified as CD20-directed cytolytic antibodies, including rituximab.
- Progressive Multifocal Leukoencephalopathy (PML): JC virus infection resulting in PML and death can occur
 in rituximab-treated patients with hematologic malignancies.
- Tumor lysis syndrome: Acute renal failure, hyperkalemia, hypocalcemia, hyperuricemia, or hyperphosphatemia from tumor lysis, some fatal, can occur within 12-24 hours after the first infusion of rituximab in patients with NHL. A high number of circulating malignant cells (≥25,000/mm3) or high tumor burden, confers a greater risk of TLS.
- Infections: Serious, including fatal, bacterial, fungal, and new or reactivated viral infections can occur during and following the completion of rituximab-based therapy.
- Cardiac arrhythmias and angina
- Renal toxicity
- Bowel obstruction and perforation

Cytopenias

6.3 Ifosfamide

In clinical trials of ifosfamide monotherapy, the most common (≥10%) adverse reactions were alopecia, nausea/vomiting, leukopenia, anemia, CNS toxicity, hematuria, and infection.

According to the package insert for ifosfamide, ifosfamide can cause:

- Myelosuppression: Can be severe and lead to fatal infections.
- Neurotoxicity: Severe and fatal neurotoxicity can occur. Carefully monitor the patient for CNS toxicity and other neurotoxic effects.
- *Urotoxicity:* Severe nephrotoxicity with renal failure and death can occur. Monitor for nephrotoxicity with serum and urine chemistries. Mesna should be used to reduce hemorrhagic cystitis.
- Cardiotoxicity: Arrhythmias, other ECG changes, and cardiomyopathy can occur and result in death. Use with
 caution in patients with cardiac risk factors and in patients with preexisting cardiac disease. The risk of
 cardiotoxicity is dose dependent.
- Pulmonary toxicity: Interstitial pneumonitis, pulmonary fibrosis, and other forms of pulmonary toxicity with fatal outcomes can occur. Monitor for signs and symptoms of pulmonary toxicity and treat as clinically indicated.
- Secondary malignancies as late sequelae have occurred.
- Veno-occlusive Liver Disease.
- Pregnancy: Can cause fetal harm. Women should not become pregnant and men should not father a child during therapy.
- Effects on Fertility. Sterility may be irreversible in some patients.
- Anaphylactic/anaphylactoid reactions have been reported.
- Impairment of wound healing.
- Nursing: Ifosfamide is excreted in breast milk.

6.4 Carboplatin

According to the package insert for carboplatin, carboplatin can cause:

- Hematologic Toxicity: Bone marrow suppression is the dose-limiting toxicity of carboplatin. Thrombocytopenia with platelet counts below 50,000/mm³ occurs in 25% of the patients; neutropenia with granulocyte counts below 1000/mm³ occurs in 16% of the patients; leukopenia with WBC counts below 2000/mm³ occurs in 15% of the patients. The nadir usually occurs about day 21 in patients receiving single-agent therapy. By day 28, 90% of patients have platelet counts above 100,000/mm³; 74% have neutrophil counts above 2000/mm³; 67% have leukocyte counts above 4000/mm³.
 - Anemia with hemoglobin less than 11 g/dL has been observed in 71% of the patients who started therapy with a baseline above that value. The incidence of anemia increases with increasing exposure to carboplatin. Transfusions have been administered to 26% of the patients treated with carboplatin.
 - Bone marrow depression may be more severe when carboplatin is combined with other bone marrow suppressing drugs or with radiotherapy.
- Gastrointestinal Toxicity: Vomiting occurs in 65% of the patients and in about one-third of these patients it is severe. Nausea alone occurs in an additional 10 to 15% of patients. Both nausea and vomiting usually cease within 24 hours of treatment and are often responsive to antiemetic measures. Emesis was increased when

- carboplatin was used in combination with other emetogenic compounds. Other gastrointestinal effects observed frequently were pain, in 17% of the patients; diarrhea, in 6%; and constipation, also in 6%.
- *Neurologic Toxicity:* Peripheral neuropathies have been observed in 4% of the patients receiving carboplatin with mild paresthesias occurring most frequently.
 - Clinical ototoxicity and other sensory abnormalities such as visual disturbances and change in taste have been reported in only 1% of the patients. Central nervous system symptoms have been reported in 5% of the patients and appear to be most often related to the use of antiemetics.
- Nephrotoxicity: Development of abnormal renal function test results is uncommon, despite the fact that
 carboplatin, unlike cisplatin, has usually been administered without high-volume fluid hydration and/or
 forced diuresis. The incidences of abnormal renal function tests reported are 6% for serum creatinine and
 14% for blood urea nitrogen (10% and 22%, respectively, in pretreated ovarian cancer patients). Most of
 these reported abnormalities have been mild and about one-half of them were reversible.
- Hepatic Toxicity: The incidences of abnormal liver function tests in patients with normal baseline values were reported as follows: total bilirubin, 5%; SGOT, 15%; and alkaline phosphatase, 24%; (5%, 19%, and 37%, respectively, in pretreated ovarian cancer patients). These abnormalities have generally been mild and reversible in about one-half of the cases, although the role of metastatic tumor in the liver may complicate the assessment in many patients.
- *Electrolyte Changes:* The incidences of abnormally decreased serum electrolyte values reported were as follows: sodium, 29%; potassium, 20%; calcium, 22%; and magnesium, 29%.
- Allergic Reactions: Hypersensitivity to carboplatin has been reported in 2% of the patients. These allergic
 reactions have been similar in nature and severity to those reported with other platinum- containing
 compounds, ie, rash, urticaria, erythema, pruritus, and rarely bronchospasm and hypotension. Anaphylactic
 reactions have been reported as part of postmarketing surveillance. These reactions have been successfully
 managed with standard epinephrine, corticosteroid, and antihistamine therapy.
- Injection Site Reactions: Injection site reactions, including redness, swelling, and pain, have been reported during postmarketing surveillance. Necrosis associated with extravasation has also been reported.
- Other Events: Pain and asthenia were the most frequently reported miscellaneous adverse effects; their relationship to the tumor and to anemia was likely. Alopecia was reported (3%). Cardiovascular, respiratory, genitourinary, and mucosal side effects have occurred in 6% or less of the patients. Cardiovascular events (cardiac failure, embolism, cerebrovascular accidents) were fatal in less than 1% of the patients and did not appear to be related to chemotherapy. Cancer-associated hemolytic uremic syndrome has been reported rarely.
 - Malaise, anorexia and hypertension have been reported as part of postmarketing surveillance.
- Pregnancy: Carboplatin may cause fetal harm when administered to a pregnant woman. Carboplatin has been shown to be embryotoxic and teratogenic in rats. There are no adequate and well-controlled studies in pregnant women.

6.5 Etoposide

The most common adverse reaction is neutropenia.

According to the package insert for etoposide, etoposide can cause:

- *Myelosuppression:* Etoposide causes myelosuppression that results in thrombocytopenia and neutropenia. Fatal infections and bleeding have occurred.
- Secondary Leukemias: Secondary leukemias have occurred with long term use of etoposide.

- *Hypersensitivity Reactions:* Etoposide can cause hypersensitivity reactions, including rash, urticaria, pruritus, and anaphylaxis.
- *Embryo-Fetal Toxicity:* Based on animal studies and its mechanism of action, etoposide can cause fetal harm when administered to a pregnant woman.
- Lactation: There is no information regarding the presence of etoposide in human milk or its effects on breastfed infant milk production. There is a potential for serious adverse reactions in nursing infants from etoposide.
- Infertility: Etoposide may result in permanent loss of fertility.
- Gastrointestinal Toxicity: Nausea and vomiting are the major gastrointestinal toxicities. The severity of
 nausea and vomiting is generally mild to moderate, with treatment discontinuation required in 1% of
 patients.

Other clinically important adverse reactions in clinical trials were:

- Gastrointestinal: abdominal pain, constipation, dysphagia.
- General: fever.
- Ocular: transient cortical blindness, optic neuritis.
- Respiratory: interstitial pneumonitis/pulmonary fibrosis.
- Skin: pigmentation, radiation recall dermatitis, Stevens-Johnson syndrome, and toxic epidermal necrolysis.
- Neurologic: seizure, aftertaste.
- Hepatobiliary disorder: hepatotoxicity.

7.0 DOSE DELAY / MODIFICATION GUIDELINES

7.1 Dose Delay / Modification

- o Toxicities will be graded using the NCI CTCAE v 5.0.
- o Baseline values are from the last values obtained prior to treatment.
- When attribution of a toxicity is unclear due to overlapping toxicity profiles of the drugs included in protocol therapy (e.g. hematologic, infections, febrile neutropenia), administration of R-ICE should be prioritized since it is the standard of care and as the use of polatuzumab vedotin as part of salvage therapy remains investigational. Therefore, dose reduction/delay of polatuzumab vedotin should be attempted before dose reduction/delay of agents included in R-ICE.
- o If one agent is held due to toxicity for a given cycle, administration of the delayed agent should resume once the toxicity is resolved on the same schedule with the next cycle of combination therapy.
- o If one agent is permanently discontinued, then the participant may continue with other agent(s). Refer to Section 5.6.
- If all agents are held together due to toxicity and the delay lasts > 6 weeks, then protocol therapy will be discontinued.

o Polatuzumab vedotin

- Dose delay/modification guidelines for polatuzumab vedotin-related toxicity are described in Table 7.1.
- If a delay due to toxicity lasts > 6 weeks, permanently discontinue polatuzumab vedotin.
- Doses reduced for polatuzumab vedotin-related toxicity should not be re-escalated without discussion with the Study PI.

• Dose reductions below 1.4 mg/kg are not permitted, and toxicities should be managed with dose delays or polatuzumab vedotin should be permanently discontinued.

o R-ICE

- Dose modifications for rituximab are not permitted.
- Dose modifications/ discontinuation of ifosfamide, carboplatin, and etoposide, whether or not they are due to toxicity are permitted at the investigator's discretion/ institutional standards.

Table 7.1 Dose Modifications for Polatuzumab Vedotin

Toxicity	Polatuzumab Vedotin Dose Management Guidelines
Peripheral Neuropathy	
Grade 1 Asymptomatic; clinical or diagnostic observations only; intervention not indicated	Continue at same dose level
Grade 2/3 G2:Moderate symptoms; limiting instrumental ADL G3: Severe symptoms; limiting self care ADL; assistive device indicated	Withhold until toxicity resolves to ≤ Grade 1, then resume treatment at 1.4 mg/kg See above for guidance if the participant dose is already 1.4 mg/kg.
Grade 4 Life-threatening consequences; urgent intervention indicated	Discontinue polatuzumab vedotin
Infusion Related Reaction	
Grade 1/2 G1: Mild transient reaction; infusion interruption not indicated; intervention not indicated G2: Therapy or infusion interruption indicated but responds promptly to symptomatic treatment (e.g., antihistamines, NSAIDS, narcotics, IV fluids); prophylactic medications indicated for <=24 hrs	 Refer to Section 5.14 for supportive care Maintain same dose level during subsequent cycles
Grade 3 Prolonged (e.g., not rapidly responsive to symptomatic medication and/or brief interruption of infusion); recurrence of symptoms following initial improvement; hospitalization indicated for clinical sequelae	 Refer to Section 5.14 for supportive care Polatuzumab vedotin may be restarted at the same dose level per Investigator's discretion with prophylaxis premedication (Section 5.14). Otherwise, permanently discontinue polatuzumab vedotin.
Grade 4 Life-threatening consequences; urgent intervention indicated	 Refer to Section 5.14 for supportive care Discontinue polatuzumab vedotin
Other unspecified non-hematologic	
Grade 1/2	Continue at same dose level
Grade 3	Withhold dose until toxicity is ≤ Grade 2, then resume treatment at the same dose level. - Note: Patients who develop Grade 3 electrolyte laboratory abnormalities may continue study treatment without interruption.
Grade 4	Discontinue polatuzumab vedotin - Note: Patients who develop Grade 4 electrolyte laboratory abnormalities should have correction to Grade 3 prior to treatment resumption at the same dose.
Hematologic	
Grades 1-2	Continue at same dose level
Grade 3-4	 Withhold until toxicity resolves to ≤ Grade 2

Toxicity	Polatuzumab Vedotin Dose Management Guidelines
	 NOTE: Patients who develop Grade 3 or 4 lymphopenia may continue study treatment without interruption Growth factor support (G-CSF or GMCSF) for neutropenia should be considered for subsequent cycles, if not already given. First occurrence: resume at same dose level Second occurrence: For any toxicity (including neutropenia despite the use of G-CSF), dose reduction to 1.4 mg/kg should be considered If the participant is already receiving 1.4 mg/kg, dose discontinuation should be considered.

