5.14 Supportive care

With the exception of prohibited therapies (Section 5.13), participants should receive prophylactic or supportive as clinically indicated per institutional policies.

Prophylaxis for infusion-related reactions

- Patients should be pre-medicated with at least an anti-histamine and antipyretic (e.g. 50-100 mg diphenhydramine, 500-1000 mg oral acetaminophen) prior to all rituximab and polatuzumab vedotin infusions, per institutional standards.
- If not already pre-medicated for rituximab administration, administer an antihistamine and antipyretic at least 30 to 60 minutes prior to Pola infusion for potential infusion-related reactions.

Blood products and growth factors

- Platelet and/or red blood cell supportive growth factors or transfusions
- Permitted when applicable. For growth factors, the use of biosimilars is allowed.
- Colony stimulating factors (CSFs) (The use of biosimilars is allowed).
- Salvage: All patients should receive G-CSF with each PolaR-ICE cycle. The schedule and G-CSF formulation are per investigator discretion.
- Consolidation: Per investigator's discretion and institutional practice.

Anti-emetic prophylaxis

• Routine anti-emetic prophylaxis regimen should be administered per institutional standards.

Prophylaxis for hemorrhagic cystitis

• Mesna is to be administered with ifosfamide according to institutional standards (e.g. 5000 mg/m² on Day 2 (inpatient schedule) or 1670 mg/m² on Days 1-3 (outpatient schedule)).

Corticosteroids

- Topical, ocular, intra-articular, intranasal, and inhalational corticosteroids (with minimal systemic absorption)
- Permitted
- Systemic corticosteroids
- Physiologic replacement doses permitted even if > 10 mg/day prednisone or equivalent.
- Brief course of corticosteroids (< 3 weeks)
- Permitted for prophylaxis (e.g. contrast dye allergy)
- Permitted for treatment of non-autoimmune conditions (e.g, delayed-type hypersensitivity reaction caused by contact allergen)

Management of infusion related reactions

- Grade 1-2:
- Slow or hold infusion
- Give supportive treatment*
- Upon symptom resolution, may resume infusion (rate escalation at the investigator's discretion**)
 Note: for Grade 2 wheezing or urticaria, patient must be premedicated for any subsequent doses. If symptoms recur, the infusion must be stopped immediately and study drug permanently discontinued.
- Grade 3:
- Discontinue infusion
- Give supportive treatment*

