- Upon symptom resolution, may resume infusion (rate escalation at the investigator's discretion**)
 Note: if the same adverse event recurs with same severity, treatment must be permanently discontinued.

 Note: for Grade 3 hypotension or fever, patient must be premedicated before re-treatment. If symptoms recur, then study drug must be permanently discontinued.
 - *Note*: if patient has Grade 3 wheezing, bronchospasm, or generalized urticaria at first occurrence, study drug must be permanently discontinued.

- Grade 4:
- Discontinue infusion immediately, treat symptoms aggressively, and permanently discontinue study drug.
- * Supportive treatment: patients should be treated with acetaminophen/paracetamol and an antihistamine such as diphenhydramine if they have not been received in the previous 4 hours. IV saline may be indicated. For bronchospasm, urticaria, or dyspnea, patients may require antihistamines, oxygen, corticosteroids (e.g. 100 mg IV prednisolone or equivalent), and/or bronchodilators. Patients with hypotension who require vasopressor support must be permanently discontinued from study drug.
- ** Infusion rate escalation after re-initiation: upon complete resolution of symptoms, the infusion may be resumed at 50% of the rate achieved prior to interruption. In the absence of infusion-related symptoms, the rate of infusion may be escalated in increments of 50mg/hour every 30 minutes.

P-gp inhibitors

Closely monitor for AEs when administered concomitantly with polatuzumab vedotin.

Anti-viral and anti-pneumocystis prophylaxis

• Routine anti-viral (coverage for HSV and VZV) and anti-pneumocystis prophylaxis is required beginning at the initiation of study treatment and continuing for at least 6 months after completion of study treatment, per institutional standards. If clinically indicated, anti-infective prophylaxis for other infectious agents is permitted. For patients who proceed to AHCT, continue prophylaxis for at least 9 months after AHCT. If prophylaxis is held, the reasoning (e.g. renal dysfunction) must be documented.

Intrathecal prophylactic treatment for cerebral/meningeal disease

Permitted at the discretion of the investigator

Tumor lysis syndrome (TLS) prophylaxis and management

Permitted at the discretion of the investigator, per institutional standards
 For patients that are considered at risk for TLS [e.g. bulky disease, or high LDH (≥ 1000 IU/L) at baseline,

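### Table 7.1 leaves restart of Pola after a Grade 3 infusion reaction to discretion without exception, while Section 5.14 requires a permanent stop for several of these reactions

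*Combined protocol and SAP*

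**What the plan says.** Two places tell a site what to do with Pola after an infusion-related reaction.

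**Section 7.1, Table 7.1.** The text of Section 7.1 sends the reader to this table for delays and modifications due to Pola toxicity. In the Grade 3 infusion-reaction row the first bullet refers to Section 5.14 for supportive care. The second reads "Polatuzumab vedotin may be restarted at the same dose level per Investigator's discretion with prophylaxis premedication (Section 5.14", and adds that Pola is otherwise stopped permanently. The Grade 1/2 row refers to Section 5.14 for supportive care and then says "Maintain same dose level during subsequent cycles". The Grade 4 row stops Pola.

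**Section 5.14, management of infusion-related reactions.** For Grade 3 the general rule allows the infusion to resume once symptoms resolve. Notes then limit it:

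- "if patient has Grade 3 wheezing, bronchospasm, or generalized urticaria at first occurrence, study drug must be permanently discontinued"
- "if the same adverse event recurs with same severity, treatment must be permanently discontinued"
- "for Grade 3 hypotension or fever, patient must be premedicated before re-treatment", and if symptoms come back, "then study drug must be permanently discontinued"

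A footnote on supportive treatment adds a permanent stop for hypotension that needs vasopressors, without tying it to a grade. For Grade 2 wheezing or urticaria, later doses need premedication, and then: "If symptoms recur, the infusion must be stopped immediately and study drug permanently discontinued".

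Section 5.9.1 also points to Section 5.14 for infusion and hypersensitivity reactions. No sentence says which section governs if they differ.

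**The concern.** For the same patient, one section grants discretion and the other removes it. The clearest case is a first Grade 3 bronchospasm during Pola: Table 7.1 allows restart at the same dose with premedication, and Section 5.14 forbids any further dose.

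What is at stake is patient safety. The reactions on the mandatory list are airway and generalized allergic-type reactions, severe events that come back, and hypotension serious enough for vasopressors. Re-exposure is the hazard that the stop rules address. A dosing decision naturally starts at the dosing table, whereas the stop rules sit in notes under supportive care. An investigator who restarts Pola after such a reaction would comply with the table and breach Section 5.14.

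**Working it through.** No arithmetic bears on the core point. The check is to set the two sections side by side by clinical situation.

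| Situation | Section 5.14 | Table 7.1 | Consistent? |
|---|---|---|---|
| First Grade 3 wheeze, bronchospasm or generalized urticaria | Permanent stop | Restart allowed at discretion | No |
| Grade 3 event returning at the same severity | Permanent stop | Still Grade 3, so restart allowed | No |
| Symptoms returning after Grade 3 hypotension or fever | Permanent stop | Restart allowed if the repeat is Grade 3; no stop stated if lower | No |
| Hypotension needing vasopressors | Permanent stop, no grade given | Stop if graded 4; restart allowed if graded 3 | Depends on grading |
| Grade 2 wheezing or urticaria that returns | Permanent stop | Dose maintained; silent on stopping | Stop not stated |
| Other first Grade 3 reaction | May resume after resolution | Restart allowed | Yes |
| Grade 4 reaction | Permanent stop | Permanent stop | Yes |

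**Do the row's citations of Section 5.14 import the stop rules?** As worded, no. The first citation is for supportive care. The second is attached to premedication and tells the site how to restart, not when restart is barred. The closing instruction to stop otherwise is the alternative when the investigator chooses not to restart; it names no reaction for which stopping is required.

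**Does the table normally leave exceptions to other sections?** No. It prints exceptions in the row for Grade 3 and Grade 4 electrolyte abnormalities and for Grade 3 or 4 lymphopenia. The hematologic row also separates first from second occurrences. A reader can fairly take a row with neither feature to have no exception and to cover repeat events.

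**How many patients?** The documents give no Grade 3 rate. Table 6.2 reports infusion-related reactions of any grade in 18% of 45 patients on Pola plus BR and 8% of 39 on BR. Table 6.1, the list of expected serious reactions to Pola, does not include infusion reaction, although it lists events as rare as 2 of 635. Neither source yields a Grade 3 frequency for this regimen.

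**Effect in the safety lead-in.** Section 11.2 exempts a Grade 3 infusion reaction that settles to Grade 1 or better within 24 hours from unacceptable toxicity. Section 12.2 requires full-dose Pola over the first 2 cycles for evaluability unless an unacceptable toxicity occurs. It follows that:

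- restart, with the other dose requirements also met and no other unacceptable toxicity: evaluable, no event;
- permanent stop before full dosing, with no other unacceptable toxicity: not evaluable, and replaced under Section 12.2.

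With five treated and no events, the first path gives 0/5, which meets rule 2 of Section 12.1.1. The second gives 0/4, so one more evaluable patient is needed.

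**The case against.** The best reply is that the two sections can be reconciled. Table 7.1 permits restart and never requires it. Section 5.14 states much the same general rule for Grade 3 and then attaches specific prohibitions. A specific prohibition ordinarily limits a general permission, and stopping satisfies both sections. The row cites Section 5.14 twice and Section 5.9.1 cites it without restriction, so a site that follows the references reaches the stop rules. This stands in part: it lowers the practical risk and shows that the rule exists. It does not remove the conflict, because the permission carries no limit in the row and the plan states no order of precedence.

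The Grade 1/2 point is weaker. Keeping the dose level says that no reduction is needed; it does not say that treatment continues after a recurrence. The row omits a stop rather than contradicting one.

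Two stronger readings are tempting, and the documents do not support them.

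- A reader might infer from the table's Grade 3 description, "recurrence of symptoms following initial improvement; hospitalization indicated for clinical sequelae", that the row expressly licenses re-challenge after repeat reactions, or that recurrent Grade 2 wheezing would be regraded to 3 and so become restartable. The phrase describes severity and most naturally means relapse within one reaction. No section sets out the regrading step. The conflict on repeat Grade 3 events does not need it, since a second Grade 3 event falls in the row by its grade.
- A reader might infer that the inconsistency could reverse a dose-level decision in the lead-in. That would take two unrelated unacceptable toxicities, a particular number treated, and a decision made before the non-evaluable patient is replaced. Section 12.2 provides for replacement, so this is a remote construction and not a consequence to rely on.

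**Conclusion.** The inconsistency is real and should be corrected. For a first Grade 3 wheeze, bronchospasm or generalized urticaria, and for the recurrences listed in Section 5.14, the dosing table permits what the supportive-care section forbids. Vasopressor-dependent hypotension joins them when it is not graded 4. The plan has the right rule; the table fails to carry it.

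The size is modest and lies in safety. The number of patients affected cannot be given. The sample size, error rates and primary analysis do not depend on the point, and the lead-in effect is normally one replacement.

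The conclusion assumes that the term study drug in Section 5.14 includes Pola, which Table 7.1's own references to that section support. It also assumes that some sites will take the dosing table as sufficient for a restart decision.

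**What to change.** Three edits to Section 7.1:

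1. In the Grade 3 infusion-reaction row, after the restart permission, add: *except where Section 5.14 requires permanent discontinuation (first Grade 3 wheezing, bronchospasm or generalized urticaria; recurrence at the same severity; recurrence after Grade 3 hypotension or fever; hypotension requiring vasopressors)*.
2. In the Grade 1/2 row, add: *except recurrent Grade 2 wheezing or urticaria, see Section 5.14*.
3. State that Section 5.14 governs if it and Table 7.1 differ.

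The cost is two clauses and one sentence. No visit, procedure or new policy is added, because the edits only carry existing stop rules into the table. A lead-in patient who is stopped under Section 5.14 and is not evaluable is handled by the replacement rule already in Section 12.2.
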